- Lund Mackay score ≥ 12 (maximum 24) of sinus computed tomography (CT) or cone beam (CBCT) scans. The new sinus CT/CBCT scans are needed if the previous sinus CT/CBCT scans have been performed over 36 months before recruitment visit and it is clinically indicated, or if there is a suspicion of complication of CRS (f.ex. mucocoele, invasive fungal rhinosinusitis). Pregnant and breast-feeding subject will be excluded. Females of Reproductive Potential (FRPs) who are not pregnant or breast-feeding may be enrolled. FRPs need to perform pregnancy test prior to the CT/CBCT scans. If subject is already on contraception prior to the study this should be continued. The data of previous sinus CT/CBCT scans will be used if previous sinus CT/CBCT scans have been performed ≤ 36 months prior to recruitment visit. The clinical information of sinus CT/CBCT scans is critical to enrolling appropriate subjects for the research and cannot readily be obtained another way. The radiation dose of sinus CT/CBCT scans is less than 0.1 mSv, which corresponds to less than 10 days of natural background radiation in Finland. The increased cancer risk is minimal.
- ≥ 1 previous CRS-surgery. Note that the last CRS-surgery must have been performed at least 6 months before 1st visit
- SNOT-22 ≥ 25
- At least one other symptom, such as partial loss of smell (hyposmia), nasal obstruction, total loss of smell (anosmia), or anterior or posterior rhinorrhea
- patient should have a history of at least one exacerbation during the past two years e.g. at least one criterion must be fulfilled of the following list during the past two years ≥ 1 oral corticosteroids; ≥ 3 antibiotic courses; ≥ 1 CRS-operation; ≥ 1 asthma hospitalization. In patients with contraindications of previously listed treatment or continuous oral steroids, additional criteria are not required.
- Asthma diagnosis (patient has the National Social Insurance Institution's reimbursement right for asthma medication)
- Peripheral blood eosinophils (PBEos) > 300 cells/ μ l at visit 1 OR (PBEos > 150 cells/ μ l at visit 1 AND a history of PBEos > 300 cells/ μ l during the past 12 months). A history of Nasal polyp tissue eosinophilia (NPeos) $\geq 30\%$ during the past 12 months is a supportive criterion.

The two treatment arms, s.c. Mepolizumab and s.c. placebo injections are randomized in a ratio of 1:1 of the study patients and is scheduled 2-4 weeks before start of trial medication.

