ASA challenge is conducted during the second visit if needed, according to modified international protocol (15-16). FEV1 should be at least 1.5 L and > 60% of predicted before challenge or desensitization. Patient will receive 25 mg ASA at a hospital setting. If no remarkable symptoms are seen, patient will receive 1-2 hours later another 25 mg ASA at a hospital setting.

ASA challenge positive result:

1. Naso-ocular alone: a 30 % or > increase in at least one of the following VAS (0-10 cm) scores: nasal obstruction, nasal discharge, postnasal drip, eye itching. These may exist with or without objective signs of increased nasal turbinate swelling/discharge or eye redness in examination.
2. Naso-ocular (please see 1.) and a 15% or > decline in FEV1 or in PEF (Classic reaction)
3. Lower respiratory reaction only (FEV1 or PEF declines by >20%)
4. Laryngospasm with or without 1-3 (flat or notched inspiratory curve)
5. Systemic reaction: hives, flush, gastric pain, hypotension

Patients Randomization and the treatment arms I-II occurs after 1st (or 2nd for ASA challenged) visit. The patients are randomized to two treatment arms: I) subcutaneous injections of placebo once per month for 16 weeks II) subcutaneous injections of Mepolizumab once per month for 16 weeks. Mepolizumab 100 mg / Placebo (NaCl solution)

is injected subcutaneously once per month, for a total of 16 weeks. GSK provides the randomization codes to each center.

Table1 the study protocol

| Time | -4 weeks | -2 weeks | 0 weeks | 4 weeks | 8 weeks | 12 weeks | 16 weeks | 20 weeks |
|--|---------------|----------------------|----------------|----------------|----------------|----------------|-----------------|--------------|
| Visit | 1 | 2 | 3 | 4 | 5 | 6 | 7 | 8 |
| | Rekrytointi | ASA-aslustus | 1. pistoskerta | 2. pistoskerta | 3. pistoskerta | 4. pistoskerta | Seurantakäynti | Loppukäynti |
| Name of the visit | Recruitment | ASA-challenge | 1st injection | 2nd injection | 3rd injection | 4th injection | Follow-up visit | End of Trial |
| Informed Consent | x | | | | | | | |
| Review Inclusion / Exclusion Criteria | x | x No flu 2 we before | x | | | | | |
| Medical History comorbidities | x | | | | | | | |
| Randomization | x | x | | | | | | |
| Visiting Doctor | x | x | x | x | x | x | x | x |
| Visiting Nurse | x | x | x | x | x | x | x | x |
| Review of Concomitant Medication | x | x | x | x | x | x | x | x |

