| Visits, hospitalisations, exacerbations, sick leave, productivity | Previous year | | | | | | | |
| Allergy test = serum specific IgE test (pölyerittely) | x | | | | | | | |
| | x | | | | | | x | |
| ASA challenge test (to subjects without previous challenge-test-confirmed NERD dg) | | x | | | | | | |
| Treatment with IMP | | | x | x | x | x | | |
| Check side-effects | | x | x | x | x | x | x | x |
| ENT visit (+ lung examination) | x | x | x | x | x | x | x | x |
| Check CRS control | x | x | x | x | x | x | x | x |
| Pulmonologist visit | x | | | | | | x | |
| Check asthma control | x | x | x | x | x | x | x | x |
| Questionnaire-packet: SNOT-22, 15D, AQLQ, Asthma control | x | x | x | x | x | x | x | x |

| | | | | | | | | |
|---|---|----|---|---|---|---|---|-------------------|
| test, 2xNetherlands-Q | | | | | | | | |
| VAS symptoms | | x | | | | | | |
| Baseline characters questionnaire (esitietokaavake) | x | | | | | | | (x) if changed |
| Acoustic rhinometry (ARM) | x | xx | x | x | x | x | x | x |
| nNO | x | xx | | | | | x | |
| eNO | x | | | | | | x | |
| Olfaction Sniffin' sticks | x | | x | x | x | x | x | x |
| sinus CT scans | x | | | | | | | |
| Blood analysis for Biobank | x | | | - | - | - | | - |
| Blood samples (5 EDTA tubes) for metabolomics & genomics | x | xx | x | x | x | x | x | x |
| Urine samples for metabolomics | x | xx | x | x | x | x | x | x |
| Fecal sample for microbiome | x | | x | x | x | x | x | x |
| Nasal samples (microbiome, transcriptomics, histology) | x | xx | | | | | x | |
| Spirometry | x | | | | | | x | |
| PEF 1 week | x | x | | | | | x | |
| microspirometry | | x | | | | | | |
| PEF at visit | x | x | x | x | x | x | x | x |
| PNIF at visit | x | x | x | x | x | x | x | x |
| Check disease relapse | x | x | x | x | x | x | x | x |
| Consider additional therapy /referral to operation | x | x | x | x | x | x | x | x |

Study endpoints

Primary, Change from baseline

endoscopic nasal polyp score (total score ranges between 0-8 of both sides), SNOT22 symptom score, VAS score (of smell loss, obstruction, postnasal drip, nasal discharge, facial pain/pressure) and, exacerbation-rate. Exacerbation means that patient has at least one of the following due to airway symptoms: oral corticosteroid course; antibiotic courses; sinus lavation; hospitalization.

Secondary, Change from baseline

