Statistics. Data analysis will be carried out on the relationship between Mepolizumab and placebo treatment. Variables tested in the statistical models include age, gender, symptoms, exacerbations, infections, medications, endoscopic findings, sick leave, allergy, side-effects of treatment, hospitalizations, and other factors at different time-points. Student's t test (or KW, MWU tests, in case of not normally distributed sample), as well as adjusted linear regression models are used for continuous measures. A statistical analysis plan (such as correction for multiple testing) will be drawn up with advice from the statistical department at the University of Helsinki.

We will use several software: R 3.0.2, SPSS 22.0 Statistical Software Package (SPSS, Chicago, IL) and STATA (Release 13.1 software, StataCorp, Texas, USA). For comparisons, the results will be analyzed by Logistic regression, Student's t-, Chi-square, (nonparametric) Fisher's exact and Mann Whitney U test. P-values less than 0.05 are considered statistically significant. Results of logistic regression are reported as odds ratios (OR) with 95% confidence intervals. All models will be adjusted by selected covariates (potential confounding factors).

Sample handling

The samples will be stored at Helsinki Biobank or at the University of Helsinki.

Table 2. Samples and their schedule. The sample protocol is reduced in KYS and TAYS.

| Time | -8 weeks | -4 weeks | 0 weeks | 4 weeks | 8 weeks | 12 weeks | 16 weeks | 20 weeks |
|--|---------------------|---------------------------|---------------------|-------------------------|---------------------|---------------------|--|---------------------|
| Visit | 1 | 2 | 3 | 4 | 5 | 6 | 7 | 8 |
| Name of the visit | Recruitment | ASA-challenge (if needed) | 1st injection | 2nd injection | 3rd injection | 4th injection | Follow-up visit | End of Trial |
| Nasal cotton/swab samples (Microbiome, RNA) | x | xx | | | | | x | |
| Nasal biopsies under local anesthesia | X2 | x | | | | | X2 | |
| Nasopharyngeal aspirate (Microbiome) | x | | x | x | x | x | x | x |
| Fasting blood sample 18 ml ¹ | x EDTA, plasma 9 ml | xx EDTA, plasma 9+9 ml | x EDTA, plasma 9 ml | EDTA DNA 4 ml, CPT 8 ml | x EDTA, plasma 9 ml | x EDTA, plasma 9 ml | x EDTA, plasma 9 ml; EDTA DNA 4 ml, CPT 8 ml | x EDTA, plasma 9 ml |
| Biobank 0-blood sample (voluntary) | X | | | | | | | |
| Blood sample (CBC, WBC differential, S-IgE allergen profile) + ECG | X | | | | | | x | |

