The statistical analyses will be conducted in the modified intention-to-treat (mITT) population, defined as all randomized participants who received at least one dose of the investigational medicinal product and fulfilled the inclusion criteria. One randomized participant was excluded due to failure to meet inclusion criteria, resulting in 47 participants per treatment group. All analyses were performed blinded to treatment allocation, and the randomization code was opened only after the trial was closed and the primary analyses completed. The sample size was calculated to provide 80% power to detect clinically meaningful differences in the coprimary endpoints using a two-sided significance level of 0.05. Baseline was defined as the recruitment visit, occurring approximately eight weeks prior to initiation of the investigational medicinal product. Participants received four injections over a 16-week treatment period, followed by an additional eight-week observation period without treatment, after which final measurements were obtained. Continuous variables are summarized using means with standard deviations or medians with interquartile ranges, as appropriate, and categorical variables using frequencies and percentages. The coprimary endpoints and all secondary continuous outcomes were analyzed as changes from baseline using linear mixed-effects models. These models included fixed effects for treatment group, time, and their interaction, and a random intercept for participants to account for within-subject correlation over repeated measurements. Group-specific changes from baseline were estimated at each follow-up time point, and treatment effects were assessed by comparing differences in these estimated changes between groups. Results are reported as mean differences with 95% confidence intervals. A two-sided significance level of $p < 0.05$ was applied to all analyses, and no formal adjustment for multiple comparisons was performed. Model assumptions were evaluated by visual inspection of residual plots to assess normality and homoscedasticity, and by examination of fitted values and influence diagnostics to identify outliers or model instability. The linear mixed-effects modeling framework was selected because it accommodates unequally spaced measurements and missing observations and provides unbiased estimates under the missing-at-random assumption.

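### Change is measured from recruitment, about eight weeks before dosing, although SNOT-22 and several function tests are repeated at week 0: reported within-arm changes absorb pre-dose change and the arm comparison may lose some precision

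*SAP*

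**What the plan says.** **Baseline.** The SAP's statistical text says: "Baseline was defined as the recruitment visit, occurring approximately eight weeks prior to initiation of the investigational medicinal product". The protocol's endpoint list (section 2.1) refers to change from baseline without defining it. The SAP fits a linear mixed model to the changes, with group, time, their interaction and a random intercept. No baseline covariate is listed. It reports group-specific changes and takes the difference between them as the treatment effect.

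**Week-0 measurements.** Protocol Table 1 marks the questionnaire packet at all eight visits: "Questionnaire-packet: SNOT-22, 15D, AQLQ, Asthma control | x | x | x | x | x | x | x | x". PEF at visit, PNIF and acoustic rhinometry are also marked at every visit, and Sniffin' sticks at visit 1 and from week 0 onwards. An ENT visit is marked at week 0, but no legible row names polyp scoring there. Spirometry, eNO and nNO (Table 1), and the blood count and nasal biopsies (Table 2), have no week-0 entry.

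**Interval.** Table 1 begins "Time | -4 weeks | -2 weeks | 0 weeks" and Table 2 begins "Time | -8 weeks | -4 weeks | 0 weeks". Randomization, per section 2.1, "is scheduled 2-4 weeks before start of trial medication".

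**The concern.** Visit 1 is where patients qualify: SNOT-22 of at least 25, polyp score of at least 5 out of 8, and a blood eosinophil threshold. Values selected for being high tend to fall on remeasurement, so some improvement from visit 1 is expected without any drug. The interval before the first dose also contains the ASA challenge for some patients, nasal biopsies, and whatever natural drift occurs. It may also contain settling on regular nasal steroid, because the protocol times that run-in from study entry and does not define study entry.

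All of this is counted in each arm's change. A placebo-arm improvement could be read as a response during treatment, and the mepolizumab arm's own change would look larger than what happened after dosing. A more distant baseline may also be less correlated with the outcome, which widens the confidence interval for the arm difference. The trial has little precision to spare: 57 per arm were planned and 47 analysed.

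**Working it through.** **1. The plan's own figure.** Inputs from the protocol's power paragraph: difference 9, SD 17, power 0.8, alpha 0.05; two-sided from the SAP.

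n = 2 × (1.960 + 0.842)² × 17² / 9² = 56.01, rounded up to 57 per arm (t-based 56.98, also 57). Then 57 / 0.95 = 60 per arm, or 120 in total. This reproduces the plan. The paragraph also names a difference of 13, which would give only 27 (t-based 28); that is a separate point. At 47 per arm, 9 / (17 × √(2/47)) = 9 / 3.51 = 2.57, so power is 72.8%, taking SD 17 as the SD of the analysed quantity.

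**2. Assumptions from here on.** The documents give no SNOT-22 mean, no visit-to-visit correlation and no drift. I assume normality, SD 17, entry at SNOT-22 ≥ 25 on visit 1, and a range of values for the rest.

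**3. Regression to the mean within an arm.** Expected fall = (1 − ρ) × 17 × φ(a) / (1 − Φ(a)), with a = (25 − mean) / 17. For an unselected mean of 45, a = −1.18 and 17 × φ/(1 − Φ) = 3.86. Over ρ from 0.9 to 0.6:

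| Unselected mean | Expected fall (points) |
|---|---|
| 35 | 0.8 to 3.2 |
| 45 | 0.4 to 1.5 |
| 55 | 0.15 to 0.6 |

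**4. Placebo change at week 16.** Take mean 45 and an assumed 4-point pre-dose fall in both arms. From visit 1, with correlation 0.5 between visit 1 and week 16: −4 − (1 − 0.5) × 3.86 = −5.9. From week 0, with correlation 0.7 between visit 1 and week 0: (0.5 − 0.7) × 3.86 = −0.8. Simulation of 8,000 trials per setting, 47 per arm, agrees (next table).

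**5. Between-arm difference.** In the same simulations a true effect of 0 was estimated as −0.05 to +0.02, and a true effect of −9 as −9.00 to −9.06, whichever baseline was used. The expected difference does not move.

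**6. Precision.** Empirical standard error (SE) of the difference, in points. Correlations are listed as visit 1 with week 0 / visit 1 with week 16 / week 0 with week 16.

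| Assumed correlations | Placebo change from visit 1 | Placebo change from week 0 | SE, change from visit 1 | SE, change from week 0 | Ratio | SE, visit 1 as covariate |
|---|---|---|---|---|---|---|
| 0.70 / 0.50 / 0.60 | −5.9 | −0.8 | 3.34-3.39 | 3.10-3.13 | 1.07-1.09 | 3.04-3.08 |
| 0.85 / 0.70 / 0.75 | −5.2 | −0.6 | 2.64 | 2.46-2.47 | 1.07 | 2.50-2.52 |
| 0.60 / 0.30 / 0.50 | −6.7 | −1.1 to −1.2 | 3.88-3.91 | 3.44 | 1.13-1.14 | 3.34-3.35 |

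With week 0 as the covariate instead, the SEs are 2.82-2.83, 2.32-2.33 and 3.04-3.05.

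A closed form that ignores entry selection gives a similar answer: SE = 17 × √((2/47) × 2 × (1 − ρ)). With ρ = 0.57 over 24 weeks and 0.65 over 16 weeks, the SE is 3.25 from visit 1 and 2.93 from week 0. With 0.47 and 0.57 it is 3.61 and 3.25. Both pairs are a reduction of about 10%. If ρ is the same at all intervals, the two SEs are equal.

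**7. Interval.** Visit 1 to week 16 is 8 + 16 = 24 weeks under Table 2 and the SAP, but 4 + 16 = 20 weeks under Table 1. The randomization window in section 2.1 coincides with the visit 1 and visit 2 columns of Table 1.

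**The case against.** The strongest defence is that the SAP's effect measure is the between-group difference. Drift and regression to the mean act alike, in expectation, on two randomized, double-blind arms. That stands. A reader might infer that the estimated drug effect is biased; the documents do not support this.

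A reader might also take the chance between-arm difference in pre-dose drift as the error caused by the choice. From the same formula, its SD is 2.5 to 3.1 points for assumed eight-week correlations of 0.74 to 0.60, about a third of 9 points. That is the sampling SD of week 0 minus visit 1, not excess error, because a week-0 change score carries baseline noise of its own. The excess is the gap between the SEs above: roughly 0.2 to 0.5 points, or nothing under constant correlation, which is the pattern a random-intercept model implies.

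Nor are all change scores affected in the same way. For FEV1, eNO, nNO, blood count and tissue eosinophils, visit 1 is the only pre-dose value scheduled for every patient. For the polyp score, a week-0 value is only implied by the ENT visit, although one row of Table 1 has lost its label. Regression to the mean from selection concerns only entry measures and their correlates.

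Visit 1 has merit too: it precedes randomization, and week 0 does not. Adjusting for visit 1 recovers most or all of the lost precision without moving baseline. Part of the SAP was not available to me, so a stated rationale there cannot be excluded.

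What survives is that the within-arm changes are contaminated, no baseline adjustment is listed, no week-0 sensitivity analysis appears in the available text, and the interval is stated inconsistently.

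**Conclusion.** The point holds at low to moderate severity, as a cheap improvement and not a flaw that threatens the primary comparison. For SNOT-22, a coprimary endpoint, and for four function tests, a later scheduled value goes unused as baseline. The group-specific changes therefore include pre-dose change. In the illustration, placebo moves by −5.2 to −6.7 points from visit 1 against −0.6 to −1.2 from week 0; that rests on an assumed mean of 45, an assumed 4-point drift and assumed correlations. The between-arm difference is unbiased with either baseline. Its SE is about 7-14% larger with visit 1 if correlation decays as assumed, and no larger if it does not. The conflict between -4 and -8 weeks needs no assumption.

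**What to change.** 1. For SNOT-22, PEF at visit, PNIF, acoustic rhinometry and Sniffin' sticks, define baseline as the week-0 value taken before the injection. Do the same for the polyp score if it was scored at that visit. Use the visit-1 value as a covariate, or as the baseline in a sensitivity analysis. If week 0 is missing, use visit 1; do not use the ASA-challenge visit, which only some patients attend and where values may be provoked.
2. For FEV1, eNO, nNO, blood count and tissue eosinophils, keep visit 1 as baseline and add it as a covariate.
3. Wherever changes from visit 1 are reported by arm, say that they include change before the first dose.
4. Make Table 1, Table 2 and the SAP give one recruitment-to-dose interval.

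The cost is one revised definition and a re-run, with no new data for outcomes already scheduled at week 0. The downsides are that week 0 follows randomization, although it is blinded and can be taken before dosing, and that baseline timing will differ between outcomes and should be stated in each table.

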We will recruit a total of 120 patients with severe NSAID hypersensitivity, i.e., NERD, nasal polyposis and asthma in HUS, KYS, and TAYS in 2020-22. Patients will be randomized to two treatment groups in a 1:1 ratio. Group-1 receives subcutaneous placebo once monthly for 16 weeks and Group-2 receives subcutaneous Mepolizumab 100 mg once monthly for 16 weeks. The study lasts about 6 months. This first visit ensures the inclusion and exclusion criteria of the subject. If necessary, NERD will be verified by an ASA exposure test at a second additional visit. Subjects also have 6 visits, on four of which subcutaneous injection of the study product is administered. During visits, a clinical examination, airway function tests, and nasal, blood, urine, and stool samples are taken. The study aim is to elucidate the treatment and predictive biomarkers of severely symptomatic NERD patients.

2. Methods

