2.1. General

The objective of the study is to investigate the effects of Mepolizumab In the treatment of NERD with uncontrolled CRSwNP:

-Does Mepolizumab reduce endoscopic nasal polyp score and SNOT22 symptom score more than placebo?

-Does Mepolizumab reduce exacerbation-rate, reduce need for dosing-up medication, reduce signs of Th2-inflammation (such as eosinophilia) in blood and nasal samples, as well as improve lung and nasal function more effectively than placebo?

The study is performed as a randomized double-blinded prospective controlled multicenter trial. A total of 120 adult NERD patients will be recruited. The NERD with uncontrolled CRSwNP treated in our hospitals, will be systematically searched and recruited. About 70-75 NERD patients will be recruited at the Departments of Otorhinolaryngology and Allergy of Helsinki University Hospital (HUS), and the rest will be recruited at the Departments of Otorhinolaryngology, Allergy and Pulmonology of Tampere University Hospital (N=35), Kuopio University Hospital (N=10-15). The study will be monitored by a professional monitor. Electronic CRF and paper/electronic patient questionnaires provided by HUS will be used (eCRF and patient questionnaire, Granitics).

The diagnosis of CRS with nasal polyps (NP) is based on positive history, nasal endoscopy and computed tomography scans (EPOS 2012). EPOS-criteria for CRS include: Inflammation of the nose and the paranasal sinuses characterized by two or more symptoms, one of which should be either nasal blockage/obstruction/congestion or nasal discharge (anterior/posterior nasal drip): \pm facial pain/pressure, \pm reduction or loss of smell.

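### The SAP models change from baseline without adjusting for the baseline value, although the protocol says all models will be covariate-adjusted; precision is probably lost and chance baseline imbalance is over-corrected.

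*SAP*

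**What the plan says.** The SAP's statistical text states: "The coprimary endpoints and all secondary continuous outcomes were analyzed as changes from baseline using linear mixed-effects models". The model terms are given in full: "These models included fixed effects for treatment group, time, and their interaction, and a random intercept for participants". The treatment effect is then a contrast of changes: "treatment effects were assessed by comparing differences in these estimated changes between groups". No baseline value, centre or other covariate is listed. The sensitivity analyses (complete cases, and exclusion of participants given systemic corticosteroids) reuse the same models, so they do not fill the gap.

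The protocol planned otherwise. Its Statistics paragraph, under Data management, lists t tests or rank tests "as well as adjusted linear regression models are used for continuous measures", and adds: "All models will be adjusted by selected covariates (potential confounding factors". It does not say which covariates will be selected, and it leaves detail to a later analysis plan. The SAP drops the adjustment without giving a reason.

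On centres, protocol section 2.1 plans 70-75 patients at Helsinki and the rest at "Tampere University Hospital (N=35), Kuopio University Hospital (N=10-15". On allocation, the Summary says "Patients will be randomized to two treatment groups in a 1:1 ratio" and section 2.1 says "GSK provides the randomization codes to each center". Neither states stratification or blocking by centre.

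**The concern.** In a randomised trial the baseline value of the outcome is usually the most useful covariate, and here it is already collected for every participant. An unadjusted change score uses it inefficiently: it subtracts the whole baseline value, where a fitted model would subtract only the part that predicts follow-up.

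A slope below 1 is likely here. Both coprimary outcomes have an entry threshold (polyp score at least 5 of 8, SNOT-22 at least 25), and the SAP takes baseline at the recruitment visit, about eight weeks before the first injection. Some regression to the mean is to be expected.

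Two things are at stake. The first is precision, in a trial that analyses 47 per arm where the protocol planned 57. The second is the credibility of the estimate if the arms differ at baseline by chance: the arm that starts higher will tend to show the larger fall whatever the treatment does.

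**Working it through.** **Inputs from the documents.** SD 17, difference 9, power 0.80, 57 per arm, 5% discontinuation, total 120 (protocol, Power calculation); two-sided alpha 0.05 and 47 per arm analysed (SAP).

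**Assumed, because the documents do not give them.** Baseline/follow-up correlation rho from 0.4 to 0.7; equal SDs at baseline and follow-up, relaxed in step 5; 17 as the SD of change, varied in step 4. The protocol calls 17 the SD of the response and does not say whether that is the raw score or the change.

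**1. The plan's own figure.** A two-sample t test with difference 9 and SD 17 needs 56.98, so 57 per arm, and 114/0.95 = 120. The plan's figure reproduces with 9. The same paragraph also mentions 13, which would need only 28 per arm; that conflict is a separate matter. At 47 per arm, power for 9 points is 71.9%.

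**2. Variance ratio.** With common SD s:
- change score: variance 2s²(1 − rho)
- baseline-adjusted: variance s²(1 − rho²)
- ratio: (1 + rho)/2, so the variance saving is (1 − rho)/2

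A small simulation of the SAP's mixed model (47 per arm, five follow-up visits, 60 runs), with and without baseline, gave variance ratios of 0.69 at rho 0.4 and 0.85 at rho 0.7. The formula gives 0.70 and 0.85.

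**3. Consequence if 17 is the SD of change.** The unadjusted SE is 17 × √(2/47) = 3.51, and the 95% half-width is 1.986 × 3.51 = 7.0 points. The adjusted SD is 17 × √((1 + rho)/2).

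| rho | variance saving | SE and CI width saving | half-width | power for 9 points |
|---|---|---|---|---|
| unadjusted | – | – | 7.0 | 71.9% |
| 0.4 | 30% | 16% | 5.8 | 85.9% |
| 0.5 | 25% | 13% | 6.0 | 83.5% |
| 0.6 | 20% | 11% | 6.2 | 81.0% |
| 0.7 | 15% | 8% | 6.4 | 78.7% |

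**4. If 17 is the SD of the raw score.** The proportional savings are unchanged but power differs. At rho 0.4 it rises from 64.0% to 79.1%; at rho 0.7, from 90.6% to 94.5%.

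**5. Entry thresholds.** Selecting on baseline lowers its SD and the correlation together, but leaves a linear slope of follow-up on baseline unchanged. Let R be the correlation before selection (equal SDs) and k the truncated baseline SD as a fraction of the unselected one. The saving is (1 − R)k² / [(1 + R) + (1 − R)k²].
- k = 0.8: 0.384/1.784 = 22% at R 0.4; 0.192/1.892 = 10% at R 0.7.
- k = 0.6: 0.216/1.616 = 13% at R 0.4; 0.108/1.808 = 6% at R 0.7.

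**6. Conditional bias.** A chance baseline difference has SE equal to the baseline SD × √(2/47) = 0.206 baseline SDs. The change score carries −(1 − rho) of it into the estimate. If the baseline SD is 17, a one-SE imbalance is 3.5 points and shifts the estimate by 2.1 points (rho 0.4) to 1.1 points (rho 0.7), opposite in sign to the imbalance. If 17 is instead the SD of change, the baseline SD is 17/√(2(1 − rho)), the one-SE imbalance is 3.2 to 4.5 points, and the shift is 1.9 to 1.4 points.

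**7. Centre.** If centre explained 1-5% of the variance (an assumption), adjusting for it would cut the SE by 0.5-2.5%.

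**The case against.** **The size is not known for this trial.** A reader might take 15-30% as an established loss, or as a loss in CI width. Neither is supported. The documents give no correlation and no separate baseline and follow-up SDs; the range describes variance only, and the CI width changes by half as much. If one fixes the observed correlation and lets the baseline SD fall to 0.8 of the follow-up SD, the saving is 16% at rho 0.4 but 2% at rho 0.7; it vanishes where rho equals the SD ratio. This objection stands as a limit on the size. No SD or correlation is available for the polyp score, so the power figures cover SNOT-22 only.

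**The analysis is not invalid.** A reader might infer that baseline imbalance is left uncorrected, or that the treatment estimate is biased. A change score does correct for baseline, only too much when the slope is below 1, and it is unbiased over randomisations. The fault is one of efficiency and conditional bias.

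**The protocol did not promise this particular model.** That is correct. It names neither the baseline value of the outcome nor centre as a covariate to be selected. The discrepancy is that it promised adjustment and the SAP has none.

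**Centre.** A reader might infer from the supply of codes to each centre that randomisation was stratified by centre, so that centre must be in the model. The sentence describes supply, and stratification is nowhere stated.

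**Timing.** The SAP is written largely in the past tense and says the code was opened after the primary analyses were completed. Replacing the primary model after that would be a post hoc change. This stands, and it shapes the fix.

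**Conclusion.** The point holds as a discrepancy between protocol and SAP and as an avoidable loss of efficiency. The listed model omits baseline, the protocol said models would be adjusted, and adding baseline costs next to nothing in precision even where it gains little.

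Under equal SDs and an assumed correlation of 0.4-0.7, the saving is 15-30% in variance and 8-16% in SE and CI width. If 17 is the SD of change, power for 9 points at 47 per arm goes from about 72% to 79-86%. With a baseline SD truncated to 0.6-0.8 of its unselected value, the variance saving is about 6-22%, and other combinations of correlation and SD ratio bring it near zero. The conditional shift from a one-SE baseline imbalance is of the order of 1 to 2 SNOT-22 points.

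The documents do not support a claim that the unadjusted analysis is invalid, or that centre adjustment is required by the randomisation. The point would fall if a part of the SAP outside the text reviewed, whose opening part is absent, lists baseline as a covariate.

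**What to change.** Add the baseline value of the outcome and its interaction with time as fixed effects in every continuous-outcome model. Keep the unadjusted change-score model as a sensitivity analysis.

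If the randomisation codes have already been opened, do not substitute one model for the other. Report the baseline-adjusted result beside the stated model, cite the protocol's Statistics paragraph as the reason, and label it as added.

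Centre may be included as a further covariate in this three-centre trial, but the gain is probably small. The SAP should also say whether randomisation was stratified by centre. The choice of a primary time point is a separate matter that this change does not settle.

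The cost is one or two sentences in the SAP and a re-run of the models. No new data are needed.
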